# 7.5. Replacement of Subjects

In the dose-escalation part of the study, subjects without a DLT who receive fewer than 10 doses through Cycle 2, Day 15 (C2D15) will be considered unevaluable for DLT assessment and will be replaced at the same dose level if the minimum number of evaluable subjects has not been reached for the cohort. However, the subject may remain in the study if the Investigator feels the risk/benefit ratio is acceptable. There will be no replacements of subjects other than subjects who are considered unevaluable for DLT assessment.

Subjects who discontinue for any reason, including disease progression, prior to the completion of the C2D15 visit in the dose-expansion part of the study (Part B) or in the combination therapy part of the study (Part C) will be replaced.

Data from subjects who are replaced will be included in the data analysis.

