After the RP2D is determined, the second part of the study (ie, Part B) will begin. In this part of the study, up to 41 subjects with melanoma (including no more than 5 ocular melanoma subjects) and up to 41 subjects with RCC may be enrolled to receive ALKS 4230 at the RP2D. Enrollment to these cohorts will follow a PR (unconfirmed) Simon's two-stage design enrollment as outlined in Table 2. Response assessments will be based on the RECIST guidelines.

	Undesirable Rate	Desirable Rate	N1	Enroll More if	N2	Total
Expansion Cohort B1: Refractory RCC	5%	20%	21	≥2 PR/CR	20	41
Expansion Cohort B2: Refractory Melanoma a	5%	20%	21	≥2 PR/CR	20	41

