Once the safety run-in phase at the 1  $\mu$ g/kg/day dose level is complete and the SRC has agreed to proceed to the 3  $\mu$ g/kg/day dose level, the first subject will be enrolled at the 3  $\mu$ g/kg/day dose level and will be observed for 7 days as a sentinel subject. If this subject tolerates treatment adequately for 7 days, then up to 2 additional subjects may be enrolled in the following week. If the second and third subjects tolerate the 3  $\mu$ g/kg/day dose level adequately for 7 days, then 3 additional subjects can be enrolled beginning the following week.

If the first 6 subjects tolerate therapy adequately for their first 21-day cycle as assessed by the SRC, then enrollment into expansion Cohorts C1, C2, C3, and C4 will be open without restriction in the rate of enrollment at the dose determined by the SRC.

Up to 20 subjects will be enrolled into each of Cohorts C1, C2, C3 based on their tumor type and prior treatment with PD-1/PD-L1 pathway inhibitors as described in the inclusion criteria. Subjects with RCC or melanoma will not be eligible for enrollment in Cohorts C1, C2, or C3. Subjects on ALKS 4230 monotherapy in Part A or Part B who have experienced disease progression after a minimum of 2 cycles or SD after a minimum of 4 cycles and who are expected to tolerate treatment with combination therapy are eligible for treatment in Part C, Cohort C4. Subjects who have PR or CR on monotherapy are ineligible to rollover unless subsequently demonstrating progressive disease.

Subjects will receive 200 mg of pembrolizumab every 3 weeks in combination with ALKS 4230 by IV administration daily for 5 days, followed by a period off treatment of 16 days, resulting in a cycle length of 21 days (3 weeks) for each cycle.

Once a RP2D is determined for monotherapy, enrollment into Cohorts C5, C6, and C7 will open. Should monotherapy doses above 6  $\mu$ g/kg/day ALKS 4230 be shown to be tolerated, then the dose of ALKS 4230 in the combination arms may be increased. In Cohorts C5, C6, and C7, up to 53 subjects with melanoma, up to 42 subjects with NSCLC, and up to 36 subjects with squamous cell carcinoma of the head and neck may be enrolled to receive ALKS 4230 in combination with pembrolizumab at the RP2D. Enrollment to these cohorts will follow a PR (unconfirmed) Simon's two-stage enrollment as outlined below. Response assessments will be based on RECIST and iRECIST guidelines.

	Undesirable Rate	Desirable Rate	N1	Enroll More if	N2	Total

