- h In the event of Grade 4 neutropenia (where ANC <100/μL) or Grade 3 or higher febrile neutropenia the subject should be hospitalized for monitoring and assessments, managed as described in Section 9.7.
- i A pregnancy test (urine or serum) must be given to all women of childbearing potential before each treatment cycle begins. Pregnancy test results must be confirmed as negative before the first dose of each cycle is administered for all cycles. Pregnancy testing may be performed up to 72 hours prior to dosing on Day 1.
- j Tumor imaging should include all appropriate radiographic procedures to document the full extent of the subject's known disease according to RECIST and iRECIST guidelines. Assessments are to be done at the end of Cycle 2 but before the next treatment cycle. For subsequent cycles, assessments are to be done at the end of each even-numbered treatment cycle (eg, Cycles 4, 6) but before the next treatment cycle. Tumor imaging should be done during the last week of the cycle.
- k Subjects will have tumor imaging scans every 9 weeks during the Follow-up Assessment Period (until the subject discontinues from the study or starts a new therapy).
-  Anytime ALKS 4230 is administered, antipyretics should be administered prior (at least 15 minutes) to the infusion and should only be withheld at the discretion of the Investigator.
- m PK samples will be collected on Day 1 and Day 5 of Cycle 1 and Cycle 2 at predose, at the completion of the ALKS 4230 infusion, and 1, 2, 4, 8, and 16 hours after the start of the infusion. Additional samples will be collected at predose on Days 2 through 4 and on Day 6 (24 hours post Day 5 dosing). All 16-hour samples, the 8-hour sample on Day 5, and the Day 6 (ie, Day 5, 24 hour) sample are optional. For Cycle 3 and beyond, all PK samples will be collected at predose and at the end of the infusion on Days 1, 3, and 5. All PK samples should be drawn from the arm opposite of the arm used to infuse study drug. Do not take PK samples from a central line used to infuse study drug. Details regarding PK sample draw windows are provided in Table 11 in Section 8.3.10.3.

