# 14. STATISTICS

## 14.1. Determination of Sample Size

The number of subjects planned to be enrolled in this study is expected to be approximately 140 to 327. This is based on an assumption of approximately 36 to 54 subjects to be enrolled in Part A, 42 to 82 subjects to be enrolled in Part B, and up to 191 subjects to be enrolled in Part C (Table 15).

Study Period	Number of Subjects
Part A	N=36-54 (assuming 6 or 7 dose levels)
Part B	N=42-82
Part C new subjects	N=Up to 191
Part C rollover subjects	Not applicable
Part C safety run-in subjects treated at 1 µg/kg/day dose level	N=3-6
Total number of subjects exposed to ALKS 4230	N=140-327

Table 15:	Number of Subjects Expected in Each Study Period
-----------	--

Note: Part C rollover subjects do not contribute the total number of subjects exposed to ALKS 4230.

In Part A of the study, the number of subjects per dose level is illustrated in Table 1. The number of subjects to be enrolled in Part A will depend upon the number of dose escalations, which in turn will depend upon the safety profile of ALKS 4230. If 6 or 7 dose levels are enrolled, then the number of subjects participating in Part A is expected to be approximately 36 to 54.

Part B is designed to enroll subjects in each of 2 cohorts based on tumor type and prior therapy. The sample size of each cohort was chosen based on methodology described by Simon regarding optimal 2-stage designs for Phase 2 studies (Simon 1989). The intention in this study is to enroll cohorts that correspond to the first stage of such a design. The assumed alpha is 0.05 and power is 90%. Enrollment to these cohorts will follow a PR (unconfirmed) Simon's two-stage design enrollment as outlined below. Response assessments will be based on the RECIST and iRECIST guidelines.

Table 16:Simon's Two-stage Design Enrollment for Part B

	Undesirable Rate	Desirable Rate	N1	Enroll More if	N2	Total
Expansion Cohort B1: Refractory RCC	5%	20%	21	≥2 PR/CR	20	41
Expansion Cohort B2: Refractory Melanoma a	5%	20%	21	≥2 PR/CR	20	41

Abbreviations: CR=complete response, PR=partial response, RCC=renal cell carcinoma.

a No more than 5 ocular melanoma subjects may be enrolled into this cohort.

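### Part B and C subjects who stop early are replaced and drop out of the primary ORR denominator, and the enrolment caps leave no room for their replacements

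*Protocol*

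**What the plan says.** **Sizing.** Protocol 14.1 bases the expansion cohorts on Simon's optimal two-stage design. For Part B, "The assumed alpha is 0.05 and power is 90" percent; for Part C the figures are 0.15 and 85%. The tables give N1, a response count for continuing, N2 and a total. Protocol 14.5 and SAP 10 let the responses in N1 decide whether stage 2 opens. Neither says which subjects N1 counts.

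**Replacement.** Protocol 7.5 states that, in Parts B and C, "Subjects who discontinue for any reason, including disease progression, prior to the completion of the C2D15 visit" will be replaced. It adds: "Data from subjects who are replaced will be included in the data analysis". An earlier sentence in 7.5 rules out replacing anyone except subjects unevaluable for DLT; I read that as Part A only.

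**Denominator.** Protocol 14.3.3 and SAP 5.2 define the antitumor evaluable population as subjects with two completed cycles and at least one follow-up scan. Protocol 14.4.2.1 and SAP 8.1 take ORR over that population. The first scan comes at the end of Cycle 2: "Tumor imaging should be done during the last week of the cycle" (Protocol Table 6; Table 7 agrees for Part C).

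**Caps.** Protocol 8.1 allows "up to 41 subjects with RCC may be enrolled to receive ALKS 4230 at the RP2D", the same number with melanoma, and for C5 to C7 "up to 53 subjects with melanoma, up to 42 subjects with NSCLC, and up to 36 subjects" with SCCHN. The text of SAP 3.4 instead prints 31, 50 and 47 for C5 to C7, beside a table with 53, 42 and 36.

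**Criterion.** For Part B, Protocol 8.1 and SAP 3.4 say "Response assessments will be based on the RECIST guidelines". Protocol 14.1 and SAP 3.6 say "Response assessments will be based on the RECIST and iRECIST guidelines".

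**The concern.** Replacement here depends on outcome. A subject who progresses clinically, has unacceptable toxicity or withdraws before Cycle 2 Day 15 normally has no response scan. That subject would count as a non-responder among treated subjects, but is swapped for someone else and leaves the ORR denominator. ORR is a primary endpoint in Parts B and C, so a reader who takes it as the response rate of treated subjects will read it too high. Protocol 7.5 says replaced subjects' data enter the data analysis, yet no planned ORR includes them.

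The same rule leaves the two-stage scheme without a stated basis. The caps suggest that N1 and N2 count everyone entered; the replacement rule suggests that they count those who stay. The stage 1 decision commits 20 further subjects in each Part B cohort, 26 in C5, 24 in C6 and 19 in C7, so the count it uses should be written down.

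**Working it through.** **1. The plan's own figures.** The inputs are the rates, N1, continuation counts and totals in Protocol Tables 16 and 17. An exact search for the optimal design (smallest expected sample size at the undesirable rate) returns the printed N1, stage 1 count and total in every cohort. The documents print no final cut-offs; the search gives those below. The last two columns are the exact chance of continuing, P(X ≥ count) with X ~ Bin(N1, p).

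| Cohort | Rates | Stage 1 | Final cut-off (recovered) | Alpha / power | Continue, undesirable | Continue, desirable |
|---|---|---|---|---|---|---|
| B1, B2 | 5% / 20% | ≥2 of 21 | ≥5 of 41 | 0.046 / 0.902 | 28% | 94% |
| C5 | 40% / 55% | ≥12 of 27 | ≥25 of 53 | 0.149 / 0.850 | 39% | 90% |
| C6 | 13% / 27% | ≥3 of 18 | ≥8 of 42 | 0.142 / 0.853 | 42% | 90% |
| C7 | 15% / 30% | ≥3 of 17 | ≥8 of 36 | 0.144 / 0.851 | 48% | 92% |

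The stated alpha and power are met. The chance of continuing at the undesirable rate is an ordinary feature of stage 1, not the type I error.

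**2. Effect on ORR.** The documents give no replaced share q, so 5, 10 and 20% are assumed. Suppose the cohort is filled with N evaluable subjects, everyone else dosed was replaced, and no replaced subject responded. The number dosed is N/(1−q), rounded. The 29 and 8 responders are illustrative (29/53 is near 55%, 8/41 near 20%). Intervals are Clopper-Pearson 95%.

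| q | C5, 29 responders | Part B cohort, 8 responders |
|---|---|---|
| 0 (evaluable) | 29/53 = 54.7% (40.4 to 68.4) | 8/41 = 19.5% (8.8 to 34.9) |
| 5% | 29/56 = 51.8% (38.0 to 65.3) | 8/43 = 18.6% (8.4 to 33.4) |
| 10% | 29/59 = 49.2% (35.9 to 62.5) | 8/46 = 17.4% (7.8 to 31.4) |
| 20% | 29/66 = 43.9% (31.7 to 56.7) | 8/51 = 15.7% (7.0 to 28.6) |

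**3. Caps.** The caps equal N1+N2: 21+20 = 41, 27+26 = 53, 18+24 = 42, 17+19 = 36. Protocol Table 15 follows from them: 2×21 = 42 to 2×41 = 82 in Part B, and 3×20+53+42+36 = 191 in Part C. Nothing is added for replacements. At q = 10%, filling both stages with non-replaced subjects takes 41/0.9 ≈ 46, 53/0.9 ≈ 59, 42/0.9 ≈ 47 and 36/0.9 = 40.

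**4. Stage 1 rule under each basis.** If N1 and the planning rates both refer to non-replaced subjects, or both to dosed subjects, the last two columns of the first table stand. They move only when the bases differ.

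N1 non-replaced, rates per treated subject, so p becomes p/(1−q). For C5 at 10%, 0.40/0.90 = 0.444. Chance of continuing at the undesirable rate:

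| q | B | C5 | C6 | C7 |
|---|---|---|---|---|
| 5% | 30% | 48% | 46% | 52% |
| 10% | 33% | 57% | 49% | 56% |
| 20% | 38% | 78% | 58% | 64% |

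N1 all dosed, rates for subjects who stay, so p becomes p(1−q). At 10% the chance of continuing at the desirable rate falls from 94% to 91% (B), 90% to 76% (C5), 90% to 85% (C6) and 92% to 88% (C7).

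**The case against.** The plan defines one ORR denominator, and does so consistently: evaluable subjects (Protocol 11, 14.3.3 and 14.4.2.1; SAP 5.2 and 8.1). The Protocol 7.5 sentence on replaced subjects' data can be satisfied by the safety, PK and disposition analyses. Read with mandatory replacement, the natural reading is that N1 and the planning rates both refer to subjects who stay. All of this stands, and it rules out several stronger inferences:

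- A reader might infer that C5 passes stage 1 57% of the time at its undesirable rate. That needs an assumed 10% replaced share and a mismatch of bases that no passage states. On a common basis the figure is 39%. C5 is also the most sensitive cohort; Part B moves only from 28% to 33%.
- A reader might infer that two teams could report the primary ORR on different denominators. The text does not allow that. The complaint is that the single denominator leaves out early failures.
- A reader might infer that the unprinted final cut-offs, or the Protocol 14.1 sentence likening the cohorts to the first stage of a Simon design, undermine the sizing. Protocol 14.2 plans no inferential testing, and the tables with Protocol 14.5 make the two-stage operation clear. These are matters of wording.
- A reader might infer that iRECIST-only responses could decide the Part B stage 1 rule. The tables count PR/CR, iRECIST responses carry an "i" prefix, and the primary ORR is RECIST 1.1. Only the sentence in Protocol 14.1 and SAP 3.6 needs aligning.

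The timing of the first scan also limits the effect. Progression first seen on it will generally come too late to trigger replacement, so those subjects remain as non-responders.

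The objection does not reach two things: the evaluable ORR leaves out subjects who fail before their first scan, and caps equal to N1+N2 cannot hold alongside mandatory replacement when the stages are filled.

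**Conclusion.** The point holds as a reporting and consistency problem that should be fixed, not as an error in the Simon designs. At 10% replaced, ORR on all dosed subjects is 5.5 percentage points lower in the C5 example (54.7% to 49.2%) and 2.1 lower in the Part B example (19.5% to 17.4%); at 20% the gaps are 10.8 and 3.8. This assumes that replaced subjects are non-responders, which the scan schedule makes reasonable, and a replaced share that the documents do not give. The cap conflict needs no assumption about response: any replacement in a cohort that fills both stages takes it over its cap.

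The stage 1 rule has the properties in the first table if N1 and the planning rates share a basis. The plan should say that they do, because otherwise its properties can shift in either direction.

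**What to change.** 1. In SAP 8.1, add ORR with an exact 95% CI on all dosed subjects, counting replaced or unscanned subjects as non-responders, and show it beside the evaluable ORR.
2. In Protocol 14.1 and SAP 3.6, put N1/N2, the planning rates, the Protocol 7.5 rule and the caps on one basis. Either count dosed subjects in order of first dose, with replaced subjects kept as non-responders, or count retained subjects and restate the caps and Table 15 as excluding replacements. The word "enrolled" will not do, because SAP 6.2.2 dates enrolment at consent. Reconcile the 31, 50 and 47 in SAP 3.4 with its table.
3. State in Protocol 14.1 and SAP 3.6 that the Part B stage 1 rule uses unconfirmed RECIST 1.1 PR/CR, in line with Protocol 8.1 and SAP 3.4. SAP 8 derives no iRECIST endpoints.
4. If a stage 1 decision has already been taken, do not redefine it. Report the count and criterion used, and the result under the other count.

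The cost is wording and one extra table, with no new data. The reported ORR on dosed subjects will be somewhat lower. If the planning rates were meant for retained subjects, the dosed count lowers the chance of continuing at the desirable rate (C5 from 90% to 76% at 10% replaced). Choosing the retained count means planned enrolment above the present caps.

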## 14.2. General Statistical Methodology

The statistical analysis methods are described below. Additional details will be provided in the Statistical Analysis Plan (SAP) to be finalized before database lock.

In general, summary statistics (n, mean, standard deviation, median, minimum, and maximum values for continuous variables and number and percentage of subjects in each category for categorical variables) will be provided for evaluated variables. All individual subject level data will be presented as data listings.

No inferential testing procedures are planned in this study.

Data will be summarized for Part A, Part B, and Part C separately. In addition, data regarding antitumor activity for subjects in Part A who are treated at the RP2D dose may be summarized with subjects from Part B. The cumulative tumor response and AE data will be summarized for subjects who enter into the Extension Phase; additional details will be specified in the SAP.

Baseline is defined as the last value prior to the first dose of study treatment administration for each part separately.

## **14.3.** Study Populations

#### 14.3.1. Safety Population

In Part A and Part B, the safety population will include all subjects who received ALKS 4230. In Part C, all subjects exposed to ALKS 4230 or pembrolizumab will be included in the safety population. This population will be used for all safety analyses.

#### 14.3.2. Pharmacokinetic and Pharmacodynamic Population

The PK population will consist of all subjects who received at least 1 dose of ALKS 4230 and have at least 1 measurable serum concentration of ALKS 4230 at any scheduled PK time point.

The PD population will consist of all subjects who received at least 1 dose of ALKS 4230 and have at least one available postbaseline pharmacodynamics measurement.

#### 14.3.3. Antitumor Evaluable Population

The antitumor evaluable population will consist of subjects who complete 2 cycles of therapy and have at least one follow-up scan.

### 14.4. Statistical Analysis

#### 14.4.1. Subject Disposition, Baseline Demographics, and Treatment Characteristics

#### 14.4.1.1. Subject Disposition

The number of subjects in the safety population from each study part and the reasons for discontinuation will be summarized. In addition, subjects' status with regard to study treatment and follow-up will also be summarized in the Final Study Report.

#### 14.4.1.2. Demographics and Baseline Characteristics

Subject disease and baseline characteristics will be summarized using frequency distribution or descriptive statistics as appropriate.

#### 14.4.1.3. Study Treatment

The ALKS 4230 administration profile will be summarized with respect to number of cycles taken, the dose intensity, dose modifications, and reasons for deviations from the planned regimen.

#### 14.4.2. Antitumor Activity Analyses

Antitumor activity analyses will be based on the antitumor population.

#### 14.4.2.1. Overall Response Rate

The evaluation of ORR will be based on Investigator review of the radiographic or photographic images, as defined according to RECIST 1.1. In addition, central review may be assessed for select cohorts (N2 of Part B cohorts and N2 of Part C C5, C6, and C7 cohorts). Overall response

rate is defined as the proportion of subjects with objective evidence of CR or PR among the number of subjects evaluable for antitumor activity.

At the analysis stage, the best ORR will be assigned for each subject as the best response recorded after initiation of study treatment, taking into account any requirement for confirmation. If applicable, responses recorded after disease progression or initiation of new anticancer treatment will be excluded.

The ORR will be calculated separately for those subjects in the dose-escalation portion of the study (Part A), in the dose-expansion portion of the study (Part B), and in the combination therapy part of the study (Part C).

Summarization of ORR will be presented by frequency, percentage, and 95% confidence interval (CI). The CI will be obtained using an exact approach given the small sample size.

Sum of the Diameters of all lesions reported at each visit will be graphed by spider plot (% change over time) and waterfall plot (best % change). The swimmer plot will be used to display the characteristics of the responses in subjects.

#### 14.4.2.2. Immune Overall Response Rate

*The Investigator is asked to consult Seymour et al 2017 for full description of iRECIST.* iRECIST is based on RECIST 1.1. Responses assigned using iRECIST have a prefix of "i" (ie, immune) to differentiate them from responses assigned using RECIST 1.1. The principles used to establish objective tumor response are largely unchanged from RECIST 1.1, but the major change for iRECIST is the concept of resetting the bar if RECIST 1.1 progression is followed at the next assessment by tumor shrinkage.

iRECIST defines iUPD (immune unconfirmed progressive disease) on the basis of RECIST 1.1 principles. If the criteria for iUPD have never been met, principles follow RECIST 1.1. However, if the criteria for iUPD have been met, the next timepoint response could be iUPD, iSD, iPR, or iCR, or iCPD (immune confirmed progressive disease).

For iRECIST, the best overall response (iBOR) is the best timepoint response recorded from the start of the study treatment until the end of the study treatment, taking into account any requirement for confirmation. Immune overall response rate will be based on iBOR.

The iBOR will be calculated separately for those subjects in the dose-escalation portion of the study (Part A), in the dose-expansion portion of the study (Part B), and in the combination therapy part of the study (Part C). A spider plot, waterfall plot, and swimmer plot will be used to display the characteristics of the responses in subjects.

